We designed a four-week early OT intervention program for patients who have suffered a stroke with the aim of improving quality of life and facilitating their return home by providing them and their caregiver with knowledge about specific care and neurorehabilitation.

Specific Objectives

Primary outcome: Quality of life. Secondary results: Functional independence and support needs in activities of daily living, sensory-motor skills, perceptual-cognitive skills, communication skills, anxiety and depression levels.

Methods

Type and general design of the study

This is a prospective, randomized, controlled clinical trial. The population to be represented is that of patients who are discharged from the neurology service of the Virgen de la Victoria University Hospital (Malaga) and who, after medical discharge, are referred to the rehabilitation service of the Maritime Hospital of Torremolinos as outpatients by decision of the neurology and rehabilitation departments, but will not be inpatients in the Physical Medicine and Rehabilitation Unit for intensive rehabilitation.

Users who are referred to rehabilitation by obtaining a place as an inpatient, receive occupational therapy and physiotherapy daily for a period of maximum three months. However, patients who are referred to the rehabilitation service as an outpatient are taken home directly after discharge and are subsequently recalled for rehabilitation. The period that elapses from when they are discharged until they are called to begin their rehabilitation varies depending on the workload of the service, and can even be three months after discharge. Referral to external or intensive rehabilitation is made based on the rehabilitation potential, which takes into account certain criteria such as age, clinical situation and vascular injury existing at the time of discharge, social support, motivation and observed recovery. during admission. Patients assigned to the study program are included in an early occupational therapy intervention program and are compared with a control group that will receive usual care and rehabilitation.

Sample selection and size

The sample size "n" was calculated based on the main variable SAQOL-39 with the sample size determination formula for two independent groups, assuming a mean of 2.50, standard deviation of 0.75, significance level of 5%, a power of 80% and a critical difference of 0.54, obtaining a sample of 30 participants per group.

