Therefore, two groups were formed: an intervention group of 30 patients who will receive the early Occupational Therapy program in addition to the rehabilitation that they would receive independently of this study, and a control group of 30 patients who will receive the conventional rehabilitation.

Eligible patients were assigned to EOTIPS or the control group according to a pre-established computer randomized designation in blocks of six.

Inclusion and exclusion criteria

All patients must have diagnostic confirmation of stroke with single or multiple vascular lesions that had occurred in the same time period, demonstrated by neuroimaging tests (CT or MRI), be over 18 years of age, go home on discharge and live within a maximum of 30 minutes away from the hospital center, with >2 or <26 points on the National Institute of Health scale (NIHSS), 30–100 points on the Barthel Index (BI) on the second day after the stroke (with BI 100, the patient

can be included if the Montreal Cognitive Assessment is <26) and having been referred to the rehabilitation service as an outpatient. Inclusion in the study occurs prior to hospital discharge, within a two- week interval after the stroke.

Exclusion criteria are: NIHSS > 26, BI < 30, and life expectancy < 1 year. Also excluded are people with a previous stroke, dementia or other types of diseases that cause dementia and other neurological, psychiatric or medical diseases (for example, severe epilepsy, traumatic brain injury, schizophrenia, COPD, severe or unstable heart disease, sleep apnea) concomitants that could alter cognitive function, presence of moderate or severe aphasia, people who do not understand Spanish or English, as well as patients who have been referred to the Physical Medicine and Rehabilitation Unit as inpatients to receive intensive rehabilitation or who are discharged to a care home.

The variables will take into account: age, sex, educational level, marital status, nationality, mother tongue, employment, vascular territory and lesion volume.

List of results and evaluations

Patient evaluations	
Quality of life	- SAQOL-39
Level of functional independence	- BI - mRS - SIS-16
Perceptual-cognitive skills	- MoCA
Sensory-motor skills	Fugl MeyerBergTime up & go
Communication skills	- CAL
Anxiety and/or depression levels	- Berg - Hamilton

Assessments to be used in the study (all translated into Spanish)

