The following analysis model was followed: to study the differences that may exist between one group and another, before and after the intervention, a repeated measures ANOVA was carried out; to check how some variables influence others, a multivariate analysis was carried out and, finally, to know the mean and normal distribution of the variables, descriptive statistics were performed. An intragroup analysis was included by performing paired T-test studies along with Wilcolxon for non-parametric measurements. The program used for data analysis was JAMOVI (version 2.3.26).

Difficulties and limitations of the study

Regarding the limitations of this study, it is worth highlighting the biases possibly derived from the adherence to treatment of the users and their caregivers, as well as the behavior and involvement of the family member in the process that will likely induce differences in the results. It is worth highlighting the importance of the word of the patient and the caregiver due to the telephone process of the intervention, since it can lead to differences in the instructions provided by the occupational therapist and, therefore, in the treatment and final result.

Furthermore, an important limitation is the heterogeneity of the sample, since we are generally talking about patients who have had a stroke of any location, extent and volume. The random distribution of patients may result in the two groups having significant differences in the severity of their injuries or their potential for recovery. Also due to the heterogeneity of each patient's rehabilitation process, it is understood that, of the total sample size, certain patients will subsequently receive a greater number of conventional rehabilitation sessions than others, and some patients will probably not even receive any sessions. This is why it seems

interesting to subsequently study the care received by each user three months after discharge, as well as their level of functionality and quality of life.

Ethical considerations

During data collection, the anonymity of users was guaranteed. Participants will be informed of the intervention and will be asked to sign an informed consent, with participation being voluntary and allowing the user to abandon whenever they wish.

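### The plan expects a possible severity imbalance between arms, but names no severity factor in the allocation or in the between-group model, although BI and NIHSS are known at entry

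*Combined protocol and SAP*

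**What the plan says.** **Allocation.** The section on sample selection and size assigns patients by a "pre-established computer randomized designation in blocks of six". It names no stratification factor and no minimisation.

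**Eligibility.** The inclusion criteria require a BI of 30–100 on the second day after stroke (100 only if MoCA is below 26) and an NIHSS within a stated range. Inclusion comes later, before discharge and within two weeks of the stroke, so both scores exist before allocation.

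**Variables.** Those to be taken into account are "age, sex, educational level, marital status, nationality, mother tongue, employment, vascular territory and lesion volume". NIHSS is neither in this list nor in the table of evaluations. BI, mRS, Fugl-Meyer and MoCA are in the evaluation battery, which both groups complete before discharge and at three months.

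**Analysis.** The results analysis plan gives a repeated measures ANOVA for group differences before and after the intervention, and a multivariate analysis of how variables influence one another. It specifies no covariates.

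**Limitations.** Sample heterogeneity is called an important limitation, and the plan adds: "The random distribution of patients may result in the two groups having significant differences in the severity of their injuries". It extends this to potential for recovery. No step in design or analysis is tied to that risk.

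**The concern.** Blocks of six keep the arm sizes level over time. They do nothing to balance severity. With 60 patients of mixed severity, a visible difference between arms is a realistic outcome, as the plan itself says. If it happened, a positive or a null SAQOL-39 result would be open to the objection that one arm simply had better prospects, and the plan specifies no severity-adjusted comparison to answer it. The information needed is already collected as a condition of entry. A prognostic covariate would also reduce residual variance, which matters because the sample size leaves no spare power.

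**Working it through.** **1. Reproduce the plan's sample size.** The inputs are in the section on sample selection and size: "assuming a mean of 2.50, standard deviation of 0.75", and "significance level of 5%, a power of 80% and a critical difference of 0.54".

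- n per arm = 2 × [SD × (1.960 + 0.842) / difference]² = 2 × [0.75 × 2.802 / 0.54]² = 30.28, two-sided. The stated 30 reproduces to within rounding.
- At 30 per arm, SE = 0.75 × √(2/30) = 0.194. Then 0.54/0.194 = 2.79 and power is 79.6% (78.3% with the t distribution).

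**2. Chance of a severity imbalance without stratification.** The documents give no severity distribution, so the share of severe patients is an assumption. With K severe among 60 and 30 per arm, the severe count in one arm is hypergeometric (60, K, 30). The table gives the probability that the severe counts differ by at least 6 (20 percentage points).

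| Assumption | Probability |
|---|---|
| K fixed at 30 | 0.196 |
| K fixed at 29 or 31 | 0.120 |
| K fixed at 20 | 0.170 |
| K fixed at 19 or 21 | 0.095 or 0.103 |
| K varying, 50% severe on average | 0.155 |
| K varying, 30% severe on average | 0.120 |

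The difference in counts has the same parity as K. An odd K therefore needs a difference of 7 to qualify, which is why the values alternate. A fair summary is about 0.12–0.20, with some odd fixed counts near 0.10. Simulating blocks of six (40,000 trials per scenario) gave 12% with 30% severe and 15% with 50% severe.

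On a continuous severity score, the SE of the difference in means is √(2/30) = 0.258 SD. The chance of a difference of at least 0.25 SD is 0.33, and of at least 0.5 SD is 0.05.

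**3. What an imbalance does to the planned analysis.** With two time points, the group-by-time test in a repeated measures ANOVA is a comparison of changes. A severity gap of equal size at both visits cancels. What remains is:

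shift in the difference in change = imbalance in proportion severe × (mean change in severe − mean change in mild).

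The documents give no figure for the second factor. For scale, a 20-point imbalance and a differential recovery of half the planning SD (0.375) give 0.20 × 0.375 = 0.075, or 14% of 0.54. A full planning SD (0.75) gives 0.15, or 28%. Both recovery gaps are assumptions.

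**4. What adjustment would gain.** If the covariates correlate r with three-month SAQOL-39 within arms (assumption), the residual SD is 0.75 × √(1 − r²).

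| r | Residual SD | Power at 30 per arm |
|---|---|---|
| 0 | 0.750 | 79.6% |
| 0.3 | 0.715 | 83.2% |
| 0.5 | 0.650 | 89.6% |
| 0.7 | 0.536 | 97.4% |

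The comparator is the unadjusted comparison of means on which the plan was sized. Power of the change comparison depends on the pre–post correlation, which the documents do not give.

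**5. What stratification would gain.** In simulation, blocks of six within two severity strata produced no imbalance of 20 points or more. The chance of a mean difference of at least 0.25 SD fell from about 33% to 12–15%, and of at least 0.5 SD from about 5% to 0.2–0.5%. Each stratum can leave one part-filled block, an imbalance of at most 3, so the arms differ by at most 6 (33 against 27).

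**The case against.** Permuted blocks without stratification are a valid design, and the limitation is openly disclosed. Chance imbalance is already covered by the test's error rate. The plan collects lesion volume and vascular territory, and measures BI, mRS and Fugl-Meyer at baseline, so severity is not absent from the data. A multivariate analysis is mentioned. Entry is narrower than the BI range suggests, because patients go home as outpatient referrals and those with previous stroke or moderate or severe aphasia are excluded. The section on time planning says the project was completed in November 2022, so the list can no longer be changed.

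All of this stands, and it limits the point. It does not remove it, because no severity measure is named as a stratification factor or covariate, and the multivariate analysis is not tied to the between-group SAQOL-39 comparison.

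A reader might infer more than the documents support:

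- **That the result is biased.** Over repeated randomisations it is not. The cost is precision and credibility.
- **That a 20-point imbalance moves the planned estimate by 0.15.** With a 0.75 gap between severe and mild patients, that shift belongs to a raw three-month comparison. In the change comparison, only the part of the gap that arises between visits counts.
- **That stratifying would have prevented imbalance.** Differences within strata remain.
- **That the list is known to have been unstratified.** The documents are silent. They describe no factor, but do not deny one.

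**Conclusion.** The point holds as a modest, inexpensive improvement. The plan identifies severity imbalance as an important limitation, requires two severity scores at entry, and names neither in the allocation or in the between-group model. At 30 per arm, an imbalance of at least six severe patients has probability about 0.12–0.20, assuming 30–50% are severe. Its effect on the planned before-after comparison runs only through differential recovery by severity, which the documents do not allow anyone to size. The firmer argument is precision: adjustment would lift power from about 80% to about 83–97% if the correlation is 0.3–0.7, an assumption. Nothing here invalidates the randomised comparison.

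**What to change.** **For this trial.** Specify a between-group comparison of three-month SAQOL-39 adjusted for baseline SAQOL-39 and one entry-severity score (BI or NIHSS, as collected). Label it post hoc if the data have been seen. Report entry NIHSS and BI by arm, and state whether any stratification was used. The cost is one extra model and two rows in the baseline table, provided the eligibility scores were kept.

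**For the design as written, or a repeat trial.** Stratify the computer list by one two-level entry-severity factor, with separate permuted blocks in each stratum. Fix the cut-point in advance with a stated reason, and include the stratum in the between-group model. More than one such factor is impractical with 60 patients and blocks of six. The cost is a second list, up to two part-filled blocks and slightly unequal arms. No extra test or visit is needed.
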